9. STATISTICAL CONSIDERATIONS

9.1. Primary Outcome

The primary objective is to evaluate the accuracy of using the LaserSAFE technique to evaluate margin status during radical prostatectomy compared to the FFPE. The primary endpoint will be the sensitivity of LaserSAFE to detect positive margins in the posterolateral area of the prostate of more than 3 mm.

- Sensitivity will be monitored across the trial when the first 50, 150, 300 and 500 participants have been recruited.
- If sensitivity decreases below 85%, trial methodology will be reviewed and if considered appropriate by the trial will be stopped.
- This would minimise the risk of introducing an inferior alternative that would put patients at risk worse oncological outcomes

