9.3. Sample Size Calculation

The sample size was calculated to estimate the sensitivity of the LaserSAFE technique with a 95% confidence interval and a precision of $\pm 5\%$. Assuming an expected sensitivity of 91% and a positive margin prevalence of 20%, at least 126 disease-positive participants are required. This corresponds to a total of 630 participants. Allowing for up to 10% missing or non-evaluable data, the adjusted target sample size is 693 participants.

The assumptions for sample size calculations were based on the results of our previous studies where LaserSAFE demonstrated in blinded analysis of a small cohort of patients a sensitivity of 91% to detect positive margins.

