9.6.2. Primary outcome analysis

The primary analysis will evaluate the sensitivity of LaserSAFE interpretation for detecting positive surgical margins greater than 3 mm in the posterolateral prostate, using FFPE histopathology as the reference standard.

Interim analyses of sensitivity will be conducted after recruitment of the first 50, 150, 300, and 500 participants. If the observed sensitivity falls below % at any interim analysis, the trial will be stopped for futility. The final analysis will be undertaken once the target sample size of 693 participants has been reached. Sensitivity will be reported with a two-sided 95% confidence interval, calculated using the Wilson score method. Indeterminate or missing LaserSAFE results will be considered non-diagnostic and classified as false negatives in the primary analysis.

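### If the stop for low sensitivity is applied at 85%, the unadjusted 95% Wilson interval misses the planned 91% about 8–9% of the time, almost all of the excess in trials that stop early

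*Protocol*

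**What the plan says.** Section 9.6.2 sets the looks, "Interim analyses of sensitivity will be conducted after recruitment of the first 50, 150, 300, and 500 participants", and says that if observed sensitivity is too low "at any interim analysis, the trial will be stopped for futility". The copy at hand shows no figure before the percent sign in that sentence. The section then places the final analysis at 693 participants and fixes the interval: "Sensitivity will be reported with a two-sided 95% confidence interval, calculated using the Wilson score method". It names no other estimate or interval for a trial that ends at a look.

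Section 9.1 has the same four looks, "Sensitivity will be monitored across the trial when the first 50, 150, 300 and 500 participants have been recruited", and gives a threshold with a softer consequence: "If sensitivity decreases below 85%, trial methodology will be reviewed", with stopping only if judged appropriate. Section 3.3 has the same 85% and the same discretion, but lists three looks (150, 300 and 500).

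The planning values are in section 9.3: "Assuming an expected sensitivity of 91% and a positive margin prevalence of 20%, at least 126 disease-positive participants are required". From these the section derives 630 patients in all, and a 10% allowance for data loss takes the target to 693.

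**The concern.** A Wilson interval has close to its nominal coverage when the number of positives does not depend on the results. Here a low run ends the trial at a small number of positives, and only runs that stay at or above the threshold reach the full size. A low chance result early on is therefore frozen and reported, where a fixed-size trial would have gone on and partly corrected it.

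The trial has no control arm and no hypothesis test, so the sensitivity estimate and its interval are the whole primary answer. If the stated 95% is wrong, the likely harm is that a technique performing as planned is reported, after an early stop, with an interval lying wholly below its true sensitivity.

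**Working it through.** **The plan's own figure.** n = z²p(1−p)/d² with p = 0.91, d = 0.05, z = 1.96 gives 125.8, so 126 positives. 126/0.20 = 630, and 630 × 1.10 = 693. The stated figures reproduce.

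**Inputs.** True sensitivity 91% and 20% positives (9.3). Looks at 50, 150, 300 and 500 (9.1, 9.6.2) or at 150, 300 and 500 (3.3). Final analysis at 693 (9.6.2). Assumptions: stop when observed sensitivity is below 85% (3.3, 9.1); Wilson interval reported wherever the trial ends; one independent result per participant; no indeterminate readings.

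**Hand check of the first look.** 50 × 0.20 = 10 positives. 9/10 = 90% continues and 8/10 = 80% stops.
- P(X ≤ 8) = 1 − 0.91¹⁰ − 10(0.09)(0.91⁹) = 1 − 0.3894 − 0.3851 = 0.225.
- The Wilson upper limit is 94.3% for 8/10, which contains 91%, and 89.2% for 7/10, which does not.
- P(X ≤ 7) = 0.2254 − 45(0.09²)(0.91⁸) = 0.2254 − 0.1714 = 0.054.

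So the first look alone yields a misleading interval in about 5.4% of trials.

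**Whole design.** 1,000,000 simulated trials per row, with the number of positives at each stage drawn at 20%:

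| Setting, true 91% | Misses | Wholly below 91% | Wholly above 91% | Stop early |
|---|---|---|---|---|
| No stopping | 4.9% | 3.1% | 1.8% | 0 |
| Four looks, every crossing stops | 8.8% | 7.1% | 1.7% | 30% |
| Three looks, every crossing stops | 7.9% | 6.2% | 1.7% | 16% |
| Four looks, half of crossings stop | 7.6% | 5.9% | 1.7% | 18% |
| Three looks, half of crossings stop | 6.9% | 5.2% | 1.8% | 9% |

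With 10% positives and four looks the miss rate is 9.6%. With positives fixed at 10, 30, 60 and 100 at the looks, exact enumeration gives 11.1% (126 at the end) or 9.6% (139 at the end). Discreteness alone puts the no-look rate at 5.9% and 3.6% for those two sizes.

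**Where the excess sits (four looks).** Early stops: 0.304 × 21.4% = 6.5 points. Completed trials: 0.696 × 3.3% = 2.3 points. Sum 8.8%. Against no stopping, intervals wholly below the truth rise by 7.1 − 3.1 = 4.0 points, and intervals wholly above it fall slightly.

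**Check of the remedy.** Wilson at 693 and a stage-wise exact interval after an early stop:
- Positives drawn at 20%: it misses 3.5% (four looks) and 4.0% (three looks) at 91%. The largest rate at eight values checked from 80% to 95% is about 5.6%.
- Positives fixed, four looks: 4.1% (126) or 2.6% (139) at 91%, and at most about 6.4% from 80% to 95%.
- Positives fixed, three looks: 5.1% or 3.5% at 91%, and at most about 7.6%, near 94.5%. A fixed-size Wilson interval with no looks itself reaches about 6.2% at these sizes.

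**The case against.** Three objections have force.

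First, no section states a binding stop and the 85% together. Section 9.6.2 is mandatory but shows no figure, while 3.3 and 9.1 give 85% with discretion. This stands: 8.8% is the upper end for four looks at 20% positives, and the figure falls towards 4.9% as fewer crossings lead to a stop. It does not remove the point, because coverage is short of 95% at the planned sensitivity whenever a material share of crossings ends the trial.

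Second, the interval sentence follows the one placing the final analysis at 693, so it may describe completed trials only. On that reading it misses about 3.3% and is sound at 91%. The section then names nothing for the roughly 30% of trials at 91% that would stop early under four looks.

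Third, estimation after early stopping is often left to the analysis plan. But this protocol names the interval itself, and its Study Summary lets the definitive analysis plan be finalised as late as the end of recruitment, which could be after every look.

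A reader might also infer that the design makes LaserSAFE look better than it is, because weak techniques that complete report high values. At a true 82%, about 13% of completed trials do have an interval wholly above the truth, but only about 9% of trials complete. Over all trials that is about 1.3%, against about 2.0% with no looks. The stop lowers the rate of overstatement, and a rule that stops only for low values does not inflate a claim that sensitivity exceeds 85%. Nor do the documents say who sees the interim results, so nothing here rests on the looks being unmasked.

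**Conclusion.** The point holds in conditional form. If the stop is applied at 85%, the plain Wilson interval has about 91% coverage at 91% sensitivity with four looks and about 92% with three, rather than 95%. With half of crossings leading to a stop, coverage is about 92–93%. The shortfall comes from trials that stop early and lies in the direction of understating sensitivity. Trials that reach 693 are not affected at the planned value.

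The size rests on 20% positives, which section 9.3 does not tie to margins over 3 mm, and on there being no indeterminate readings. Section 9.6.2 counts those as false negatives, which would make crossings more frequent. It is worth correcting before the first look, but it comes second to settling what the stopping rule is.

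**What to change.** First reconcile sections 3.3, 9.1 and 9.6.2 on the threshold, the number of looks, and whether a crossing stops the trial or prompts a review. Then replace the interval sentence in 9.6.2 with:

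> If the trial reaches its target size, sensitivity will be given with a two-sided 95% Wilson interval. If it stops early at an interim look, sensitivity will be given as a median-unbiased estimate with an exact 95% interval based on stage-wise ordering over the looks held, with the unadjusted proportion and its Wilson interval alongside.

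The stage-wise interval should not also be used on completion. With 139 positives its upper limit sits near 97.4% whether 118, 122 or 126 are detected, which defeats the ±5% precision aim in the roughly 70% of trials at 91% that complete.

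The cost is two sentences and a short program, with no extra patients or data. After an early stop the interval is somewhat wider: for 8/10, about 44–97% against 49–94% for Wilson. The method needs a defined stopping rule; if stopping stays discretionary the interval is only approximate, and the text should say so.

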These studies required slicing the prostate margins before sampling, which required the presence of pathologist to perform and complicated subsequent pathological assessment. To overcome this, we developed LaserSAFE, a standardised technique for assessing intact specimens using FCM (25). In a pilot study, LaserSAFE demonstrated encouraging sensitivity across both expert and novice readers blinded to final histopathology results (26). More recently, we completed a feasibility study comparing LaserSAFE and NeuroSAFE, showing 91% sensitivity for detecting margins greater than 0.5 mm. However, we could not expand the feasibility study to other sites due to challenges associated with adopting NeuroSAFE in other National Health Service (NHS) centres.

The available evidence supports LaserSAFE as a promising alternative to NeuroSAFE, sharing the same underlying goal of enabling safe nerve-sparing in patients who might otherwise not receive it. The NeuroSAFE PROOF study has already demonstrated, with level 1 evidence, that this approach

can lead to improved patient outcomes (17). However, as previously reported and confirmed in our feasibility study, implementing NeuroSAFE in the NHS is not currently feasible due to the resource and time demands required.

Several important knowledge gaps must be addressed before LaserSAFE can be safely introduced into clinical practice. Unlike standard FFPE analysis, LaserSAFE evaluates tissue en face rather than in cross-section (19). This change in orientation presents a challenge for pathologists, who must adapt to interpreting margins from a new perspective. Therefore, the most critical parameter to assess is the sensitivity of the technique, as false-negative results, or failing to detect a PSM, could expose patients to adverse oncological outcomes.

An important caveat is, that evidence suggests that the length of a PSM correlates with the risk of recurrence, with margins smaller than 2 mm not associated with increased recurrence risk (27). Consequently, the NeuroSAFE protocol recommends secondary resection only when the PSM exceeds 2 mm, representing a clinically significant margin. However, margins assessed en face appear larger than those evaluated in cross-section, due to differences in orientation and tissue shrinkage during frozen or paraffin processing. Resecting small, non-significant margins could therefore compromise functional outcomes without providing oncological benefit.

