5. SAMPLING METHODS

The study will be conducted at UCLH and at least 1 other NHS centre. Participating centres will require first to have completed a site initiation visit and have experience using the Histolog Scanner as described in the training section. Potential participants will be screened from the patients referred for radical prostatectomy to the participating sites. Patient selection criteria are as follows:

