6.3.1.2. Lasersafe Technique

The LaserSAFE procedure is performed using an FCM called the Histolog[®] scanner developed by Samantree[®] which can be placed within the operating room. Histolog Scanner, Histolog Viewer, and accessories will be used according to the Instructions for Use. No modification to the CE-Mark/UKCA-Mark/FDA 510k clearance approved intended use will be made. The Histolog[®] scanner produces digital images with high, micrometre-range resolution and enables the visualization of tissue microstructures down to the cellular level. The microscope can image an area of 48x36 mm in approximately 60 seconds. Its operating principle is based on non-ionizing, low-power optical radiation (Laser) with a wavelength of 488±5 nm, and it uses a point illumination conjugated with a pinhole in front of the detector to eliminate out-of-focus signals.

The protocol of image acquisition is as follows: the prostate is cleaned using damp gauze and completely submerged in a solution that contains a photoreactive agent Histolog Dip[®] for 10 seconds. The specimen is rinsed with 0.9% NaCl solution, placed on the Histolog[®] scanner and lightly compressed using a mouldable weight. An initial live view scan confirms adequate positioning and stability of the specimen to avoid movement artefacts. If the preliminary scan is deemed satisfactory, a high-resolution digital image is acquired and stored in the microscope hard drive. The prostate is rotated to image the contralateral side. Once both posterolateral surfaces are imaged the prostate is placed in a container and fixed with formalin. Image acquisition takes less than 5 minutes. A pathologist will interpret the images on site or remotely depending on site specific requirements and complete a reporting case report form. The findings will be communicated directly to the surgeon.

Nerve sparing decisions will be guided by the result of the LaserSAFE technique.

The presence of cancer cells at the surface margin of the specimen will constitute a positive margin. Detailed results including the length of positive margin in 2 dimensions and multifocality, will be collected and included in the results.

In the presence of a posterolateral PSM, the performance of secondary resection (SR) of the ipsilateral neurovascular bundle (NVB) will be made if any of the following are present:

- (1) Multiple areas of PSM where the sum of each maximum dimension is >3 mm
- (2) any single PSM area >3 mm in maximum dimension

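### The 85% sensitivity safeguard looks only at the figure pooled over sites and pathologists, so a minority site or reader well below 85% can go unflagged

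*Protocol*

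**What the plan says.** Protocol section 5 makes the study multi-centre: "The study will be conducted at UCLH and at least 1 other NHS centre". Section 6.3.1.2 makes the index test a reading by a person: "A pathologist will interpret the images on site or remotely depending on site specific requirements and complete a reporting case report form". The number of readers and their shares of the cases are not given.

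The background (section 2) recognises that the reading task is new: "This change in orientation presents a challenge for pathologists, who must adapt to interpreting margins from a new perspective". It goes on to name sensitivity as the most critical parameter. Section 15 requires training, and at centres new to the scanner at least 25 run-in cases compared with final pathology, but sets no accuracy level to be reached.

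Section 9.3 plans for one proportion "with a 95% confidence interval and a precision of" ±5 points. Section 9.6.2 then says: "Sensitivity will be reported with a two-sided 95% confidence interval, calculated using the Wilson score method".

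Sections 3.3 and 9.1 have the methodology reviewed, and possibly the trial stopped, if sensitivity falls below 85%. The looks are at 150, 300 and 500 recruited, and 9.1 and 9.6.2 add one at 50. The threshold number is absent from the text of 9.6.2, so 85% is taken from 3.3 and 9.1. No section splits the monitored figure by site or by reader.

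**The concern.** If pathologists differ in how well they read en-face images, the pooled sensitivity is a weighted average of their results. A centre that contributes a minority of the positive margins can miss many of them while a larger, better centre holds the average above 85%. The risk table in section 10 lists a false negative that leaves a positive margin as a risk of the procedure, and 9.1 gives protection against that risk as the purpose of the rule. With no accuracy standard for entry, monitoring during the trial is the only numerical check on a new reader that the protocol describes, and it is defined only on the pooled figure.

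The summary allows the definitive statistical plan to be finalised as late as the end of recruitment. It may therefore not exist when the looks at 150, 300 and 500 take place, so what is tabulated at those looks should be settled in the protocol.

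**Working it through.** **The protocol's own figure.** Inputs from 9.3: "Assuming an expected sensitivity of 91% and a positive margin prevalence of 20" per cent, with half-width 5 points at 95% confidence.

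- n = 1.96² × 0.91 × 0.09 / 0.05² = 125.85, so 126. This matches "at least 126 disease-positive participants are required".
- 126 / 0.20 = 630, and 630 × 1.10 = 693.
- The Wilson interval at 91% of 126 is 84.7% to 94.9%, a half-width of 5.1 points.

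The calculation reproduces exactly as a single independent binomial sample, with no between-reader term.

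**Expected pooled figure with one poor site.** Site shares and sensitivities are assumed, because the protocol gives none. Pooled = share × (poor site) + (1 − share) × 91%. With the poor site at 70%:

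- 10% share: 7.0 + 81.9 = 88.9%
- 20% share: 14.0 + 72.8 = 86.8%
- 25% share: 17.5 + 68.25 = 85.75%
- 50% share: 35.0 + 45.5 = 80.5%

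Break-even, where the expected pooled figure equals 85%:

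- 20% share: (85 − 0.8 × 91) / 0.2 = 61%
- 30% share: (85 − 0.7 × 91) / 0.3 = 71%

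**How often each figure falls below 85%.** Assume the 25% share, 70% at the poor site and 91% elsewhere. Positives at each look are 20% of those recruited. Probabilities are exact binomial, and the pooled count is the sum of two binomials.

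| Look | Positives (others + poor site) | Pooled below 85% | Poor site's own figure below 85% | Same-sized site truly at 91% below 85% |
|---|---|---|---|---|
| 150 | 30 (22 + 8) | 45% | 74% | 16% |
| 300 | 60 (45 + 15) | 35% | 87% | 15% |
| 500 | 100 (75 + 25) | 35% | 97% | 18% |

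Worked cell: with 8 positives, below 85% means at most 6 detected. At 70% the probability is 1 − 0.7⁸ − 8 × 0.7⁷ × 0.3 = 1 − 0.058 − 0.198 = 0.745. At 91% it is 1 − 0.470 − 0.372 = 0.158.

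The looks are cumulative. Simulating all three together (increments 22, 23, 30 and 8, 7, 10; one million runs), the pooled figure falls below 85% at least once in 58% of trials, so it stays above at all three in 42%. The poor site's own figure falls below at least once in 98%, against 28% for a same-sized site truly at 91%.

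**The interval, as illustration only.** If the target were a population of readers, the half-width would be 1.96 × √[0.91 × 0.09 / 126 × (1 + (126/k − 1) × ICC)] for k readers with equal loads. Both k and ICC are assumed.

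- At ICC 0.05, k = 4, 6 and 10 give ±7.9, ±7.1 and ±6.3 points. Simulated Wilson coverage is 77%, 82% and 87%.
- With 4 readers, coverage runs from 90% (ICC 0.01) to 65% (ICC 0.10).

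**The case against.** The strongest objection is that nothing in 9.6.2 is wrong. A Wilson interval for one proportion is ordinary for a single-arm accuracy study, and it is valid for the average sensitivity of the readers who take part. A reader might infer that the stated 95% interval undercovers or that ±5% is a false precision. The documents do not support that. The undercoverage appears only if the target is changed to a wider population of readers, and it then rests on an ICC and reader count that the protocol does not give. The background's hope that more centres could use the technique is conditional and is not tied to the interval. Section 2 also reports encouraging pilot sensitivity in both expert and novice readers. This part of the objection stands, so the interval is not counted as an error.

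A second objection is that by-site and by-reader tables usually belong in the statistical analysis plan. That is fair for the final report, and their absence alone is not a finding. It is weaker for the looks, because that plan may be finalised after them.

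Third, the pooled rule is not silent. It fires in a third to a half of trials at each look in the example, and a poor site with half the positives pulls the expected figure to 80.5%. Uropathology expertise, image-bank training and the run-in cases also reduce the risk. This limits the claim to minority sites or readers, and it rules out saying that the safeguard cannot work.

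Fourth, by-site figures are noisy. A site truly at 91% with 6 positives shows below 85% with probability 1 − 0.91⁶ = 43%. This stands, and it is why the figures should inform a review and not trigger a stop.

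**Conclusion.** The point holds for the monitoring rule. Because the 85% safeguard sees only the pooled figure, a minority site or reader far below 85% will often not be flagged. In the example (25% of positives at 70%, the rest at 91%, 20% prevalence) the pooled figure misses the problem in about 55% to 65% of trials at any one look, and at all three in about 42%. The site's own figure would show it in 74% to 97% at a single look. The size depends wholly on the assumed share and sensitivities: the masking is stronger at smaller shares and disappears at a 50% share.

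The primary Wilson interval and the ±5% stand for the participating readers. What they lack is a statement of that scope. This is an inexpensive improvement to a safety check and does not invalidate the primary analysis.

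**What to change.** - **Section 9.1, and 9.6.2 for the looks and the final analysis:** record which pathologist read each case. At every look and at the end, tabulate sensitivity as n/N with a 95% interval by site and by reader beside the pooled figure. State that the table is for review and that there is no automatic by-site or by-reader stop.
- **Sections 9.3 and 9.6.2:** keep Wilson as the primary interval. Add a sentence that it and the ±5% apply to the participating readers and exclude between-reader variation.
- **Optional:** with enough readers, add a random-reader or beta-binomial interval as a supplement. With fewer than about five, the by-reader table is enough and no claim should go beyond those readers.

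The cost is a few sentences and a reader identifier on the existing LaserSAFE report form, where the reporting pathologist should already be traceable. No extra patients or readers are needed. The drawback is imprecise early figures: the table should show the number of positives, because a sound site with about 6 of them will show below 85% some 43% of the time.
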